6.5 Visits #4 - 5: Post-Operative Visits

All patients will have routine follow up visits after surgery. Timing of follow-up will be variable among the three groups.

- **Group A:** The surgical oncologist will see the BCT group.
 - Post-Lumpectomy 1st Post-op Visit before Radiotherapy (*1-10 weeks after lumpectomy*)
 - Post-Op Breast Q will be administered and routine imaging taken to quantify volume and mammometric parameters

- Post-Lumpectomy Post-op Visit after Radiotherapy (*6- 18 months after radiation or the latest follow-up time point within the duration confines of our study period.*)
 - Post-Op Breast Q will be administered and routine imaging taken to quantify volume and mammometric parameters

Some patients will require no adjuvant chemotherapy following lumpectomy based on their pathology. These patients are typically radiated 4-10 weeks after lumpectomy. Other patients will require chemotherapy after lumpectomy but prior to radiation. Chemotherapy duration can vary depending on selected treatment regimen but can be between 8-18 weeks excluding Herceptin which typically is administered every 6 weeks for 1 year. Patients receive Herceptin during radiation and reconstruction and so the administration of Herceptin does not independently alter any study time points. Patients will not undergo chemotherapy or radiation until after re-excision is performed in cases where there is a positive cancer margin after lumpectomy per standard of care.

[figure not shown]
- **Group B:** Mastectomy with reconstruction patients will be seen in follow up with plastic surgery.
 - Post-mastectomy 1st Post-op Visit before Completion of Reconstruction (*1-10 weeks after mastectomy*)
 - Post-Op Breast Q will be administered and routine imaging taken to quantify volume and mammometric parameters
 - Post-mastectomy Post-op Visit after Final Reconstruction (*3-8months after final reconstructive procedure or the latest follow-up time point within the duration confines of our study period.*)
 - Post-Op Breast Q will be administered and routine imaging taken to quantify volume and mammometric parameters
- **Group C:** The surgical oncologist will see the mastectomy only group.
 - Post-mastectomy 1st Post-op Visit (*1-10 weeks after mastectomy*)
 - Post-Op Breast Q will be administered and routine imaging taken to quantify volume and mammometric parameters

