 - Post-mastectomy Post-op Visit (*6- 18 months after mastectomy or the latest follow-up time point within the duration confines of our study period.*)
 - Post-Op Breast Q will be administered and routine imaging taken to quantify volume and mammometric parameters

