6.6 Variable Duration of Study Observation

Some patients may receive neoadjuvant chemotherapy prior to either lumpectomy or mastectomy. Adjuvant chemotherapy may also be required based on pathologic findings. If required, chemotherapy may begin approximately 6 weeks following surgery. Chemotherapy

duration can vary depending on selected agents but can be between 8-18 weeks. Radiotherapy if needed is usually scheduled for 6 weeks after the final chemotherapy and can last approximately 6 weeks. Treatment time may be lengthened for complications. Reconstruction procedures can happen in multiple stages, therefor extending the time to final completion. This variability in adjuvant treatment will affect the timelines for follow-up and will be recorded for study purposes.

Fig. 1. Study Arms and Duration

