8.0 DATA SUBMISSION SCHEDULE

Case Report Form	Submission Schedule
Original Consent Form	Prior to registration
Eligibility Checklist RedCap Enrollment, Visit 1, Visit 2 MRI, and Visit 3 Plastics (if applicable)	Prior to surgery
RedCap Surgical Intervention	Following receipt of final operative and pathology reports
RedCap Follow-Up Forms Post-Operative Visit 1, Oncology Course, and Post-Operative Visit 2	
Group A:
 
 ○ Post-Lumpectomy 1st post-op visit before Radiotherapy (1-10 weeks after lumpectomy) ○ Post-Lumpectomy post-op visit after radiotherapy (6-18 months after radiation or the latest follow-up time point within the duration confines of our study period.) 
Group B:
 
 ○ Post-mastectomy 1st post-op visit before completion of reconstruction (1-10 weeks after mastectomy) ○ Post-mastectomy Post-op Visit after final reconstruction (3-8 months after final reconstructive procedure or the latest follow-up time point within the duration confines of our study period.) 
Group C:
 
 ○ Post-mastectomy 1st post-op visit (1-10 weeks after mastectomy) Post-mastectomy post-op visit (6-18 months after mastectomy or the latest follow-up time point within the

	duration confines of our study period.)
Unanticipated Event via HRPO	At the time of any unanticipated event
MRI T:B ratio, Breast Q-Scores, and Vectra Mammometrics	The coordinators will ensure MRI performed, Breast-Q's completed and Vectra images captured during active patient phase. MRI T:B ratio will be performed late in the active study phase to allow for a limited number of staff to perform bulk of measurements to optimize standardization. There is also a possibility the software will be upgraded to automate the T:B ratio later in the study period. Breast-Q scores and Vectra mammometrics will be also evaluated in bulk late in the active study phase using SAS, SPSS, or another similar statistical program.

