10.3 Study Design

All DCIS, LCIS and Stage IA-IIB breast cancers that are reasonably treated with mastectomy or BCT will be screened for eligibility for participation in this study. There will be significant heterogeneity within each group in terms of presence/absence, type, timing (adjuvant/neoadjuvant) and duration of chemoradiation administered. To standardize the timing of our outcome measurement, t=0 will always be in relation to the tumor surgery (lumpectomy or mastectomy). We will also obtain a late time point for last follow-up at least 6 months after the final intervention whether therapeutic or reconstructive, whichever is last. Data collected at this late time point – relative to the initial cancer resection at t=0 – is expected

to vary substantially (months-year) between subjects. We have carefully selected IIB patients as the most advanced stage of breast cancer included. This enables us to evaluate patients with large (>5 cm) tumors that are candidates for mastectomy or BCT which will be important since it is in the larger tumors we hypothesize that patient satisfaction and mammometric data would favor mastectomy + reconstruction over BCT.

Patients that meet the inclusion criteria but who opt for mastectomy without reconstruction are included as a control group to further evaluate the impact of post-mastectomy reconstruction.

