10.5 Data Analysis

This is a longitudinal observational study to compare effects of two treatment groups on the quality of life and to explore how the treatment effects are modified by T:B ratio. For each study patient, we have a data vector $D=(\text{group}, \text{T:B ratio}, \text{location}, Q(t), 3D(t), W)$, where group is a binary indicator for two comparison groups. T:B ratio is the tumor: breast ratio measured at a continuous scale, and location is a binary indicator of tumor location. $Q(t)$ and $3D(t)$ are Q score and the VECTRA 3D generated mammometrics respectively, measured as continuous variables at $t=(0,1,2)$, where $t=0$ is the pre-treatment baseline measurement. W is a set of patient characteristics – e.g., age, obesity, stage, etc. A longitudinal study generates correlations among the repeated measurements within the same individual, and observational study often comes with a biased estimate of the treatment comparison due to confounding. These two issues, the correlation of repeated measurements and confounding, must be taken into account in the data

analysis. Regression analyses of correlated data can simultaneously address these two issues. There are two families of statistical methods for regression analyses of correlated data – mixed effect model and generalized estimating equation (GEE). Both are appropriate for our study, even though the interpretations are different – population average vs subject specific. Data analyses for our study will be performed within this framework to adjust for the patient characteristics for unbiased comparison of treatment effect and to take into account the correlations.

10.5.1 Primary objectives:

For main effect of treatment group on Q-score: fit and test a model with Q score as the dependent variable and group as the independent variable, controlling for W in the model – (Model 1).

For the difference in Q score between two treatment groups modified by T:B ratio: fit and test a model with Q score as the dependent variable, and group, T:B ratio, and group-by-T:B ratio interaction as the independent variables, controlling for W in the model – (Model 2). The results can be better presented as a graph with two lines – Q score as a function of T:B ratio for those treated with BCT, and for those treated with Mastectomy+reconstruction.

10.5.2 Secondary objectives:

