APPENDIX A: Group A — BCT + XRT ARM STUDY VISIT SCHEDULE

	Screening Oncology Surgeon	Radiology	Breast Conservation Therapy (BCT)	Postop Visit Oncology Surgeon	Final Study Visit Oncology Surgeon
	Visit #1 ²	Visit #2 ⁴	T=0	Visit #4 ⁵	Visit #5 ⁶
Past medical history ^{1,2}	X				
Physical Exam ^{2,3}	X			X	X
Informed Consent ²	X				
Discussion of therapeutic options (Breast Surgery, sentinel node biopsy, XRT &/or chemo)	X			X	
Breast-Q ² (BCT vs.)	X (Preop Vs.)			X (Post Op Vs.)	X (Post Op Vs.)
MRI ⁴		X			
Photography ²	3D			3D	3D
Documentation of lumpectomy findings ⁷			X		
Monitor for Unexpected Events			X	X	X

¹Study-relevant past medical and surgical history

²Screening procedures to be completed within 90 days of surgery.

³Baseline height, weight, clinical stage, biopsy results from pre-surgical physical examination

⁴MRI may be completed prior to Visit #1.

⁵This is done 1-10 weeks after lumpectomy where the surgical margins were cleared.

⁶Done 6- 18 months after radiation therapy has concluded or the latest follow-up time point within the duration confines of our study period.

⁷Final pathological stage, document if re-excision is needed

Note: No required Visit #3 for Group A.

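### Section 10.3 sets the late outcome at least 6 months after the last intervention, but Group B's schedule allows the final Breast-Q from 3 months after reconstruction, and Models 1 and 2 name no assessment-time term

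*Combined protocol and SAP*

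**What the plan says.** Section 10.3 states the timing rule in the course of explaining how outcome timing will be standardized: "a late time point for last follow-up at least 6 months after the final intervention whether therapeutic or reconstructive, whichever is last". It adds that this point will vary considerably between patients when counted from the cancer resection.

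The visit schedule differs for Group B (mastectomy with reconstruction). Section 6.5 gives "3-8months after final reconstructive procedure or the latest follow-up time point within the duration confines of our study period", Section 8.0 repeats it as "3-8 months after final reconstructive procedure or the latest follow-up time point within the duration confines of our study period", and footnote 6 of Appendix B agrees. For Group A (BCT), footnote 6 of Appendix A gives "6- 18 months after radiation therapy has concluded", with the same fallback to the latest available follow-up. Group C, which is outside the two-group primary models, is timed "6- 18 months after mastectomy or the latest follow-up time point within the duration confines of our study period".

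On adjuvant treatment, Section 6.6 says "chemotherapy may begin approximately 6 weeks following surgery", gives a duration of 8 to 18 weeks, and continues: "Radiotherapy if needed is usually scheduled for 6 weeks after the final chemotherapy and can last approximately 6 weeks". It also says that reconstruction may take several stages and that the variability will be recorded.

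Section 10.5 has the Q-score "measured as continuous variables at $t=(0,1,2)$, where $t=0$ is the pre-treatment baseline measurement". Model 1 lists group and the covariate set W. Model 2 adds tumor:breast ratio and its interaction with group. W is described as patient characteristics, with age, obesity and stage as examples and the list left open.

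**The concern.** The final Breast-Q is the late outcome in the comparison of BCT with reconstruction. If one group may be scored sooner after treatment than the other, and satisfaction changes over those months, part of the group difference would reflect when patients were asked rather than which operation they had.

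The primary objective asks for the tumor:breast ratio at which reconstruction becomes preferable, and the two Model 2 lines are meant to show it. A timing shift in one line would move the point where they cross. Section 10.5 itself says that confounding must be dealt with in the analysis, but names no use for the recorded timing.

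**Working it through.** The plan gives no figure for this point to reproduce. The 83 per arm in Section 10.4 does not depend on visit timing and is not at issue here.

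**Inputs.** Minimum of 6 months after the last intervention (10.3). Group B window of 3 to 8 months after the last reconstructive procedure (6.5, 8.0, Appendix B). Group A window of 6 to 18 months after radiation (6.5, Appendix A). Chemotherapy starts about 6 weeks after surgery and lasts 8 to 18 weeks; radiotherapy starts 6 weeks after chemotherapy and lasts about 6 weeks (6.6). Conversion: 52.18/12 = 4.35 weeks per month.

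**1. Do the texts refer to the same measurement?** Section 10.3 speaks of a late time point and does not name the Breast-Q. The link is its reference to outcome measurement. In addition, Appendix B labels Visit #5 the final study visit, and Section 10.5 has only three time points, so no later visit exists for 10.3 to describe.

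**2. Reconstruction is the last intervention.** The part of the window below the minimum is 6 − 3 = 3 months of 8 − 3 = 5, or 60% of its width. A visit at 6 to 8 months satisfies both texts.

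**3. Adjuvant therapy ends after reconstruction.** Let E be the months from the last reconstructive procedure to the end of adjuvant therapy. Section 10.3 then requires a visit at E + 6 or later, and the window closes at 8. An in-window date exists only if E + 6 ≤ 8, that is, E ≤ 2.

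**4. Example: reconstruction complete at mastectomy.**

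| | Chemotherapy only | Chemotherapy, then radiotherapy |
|---|---|---|
| End of treatment, weeks after surgery | 6+8 = 14 to 6+18 = 24 | 14+6+6 = 26 to 24+6+6 = 36 |
| In months | 3.2 to 5.5 | 6.0 to 8.3 |
| 10.3 minimum (+6), months | 9.2 to 11.5 | 12.0 to 14.3 |
| Beyond the 8-month close, months | 1.2 to 3.5 | 4.0 to 6.3 |

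An in-window score can thus precede the end of treatment. Later reconstructive stages move the window later and can remove this part of the conflict, leaving only step 2.

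**5. Group A.** Section 6.5 places any chemotherapy before radiation. When radiation is the last treatment, the window opens at 6 months, so every in-window date meets the 10.3 minimum.

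**6. Models.** The listed terms are group and W (Model 1), and group, ratio, group-by-ratio and W (Model 2). The index t is a visit number. Even if a visit term is intended, it would not separate a score at 3 months from one at 8 months.

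**7. Effect on the crossing point.** Write the Model 2 group difference at ratio r as b1 + b3·r. The lines cross at r = −b1/b3. A timing shift d in the contrast, equal at all ratios, moves the crossing by −d/b3. The documents give neither d nor b3, so no value can be calculated.

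**The case against.** **The fallback clause may cure the conflict.** Every group may be assessed at the latest follow-up within the study period, and Section 6.8 foresees 12 months to 4.5 years of follow-up. On that reading a Group B patient with later adjuvant therapy could be scored late enough for both texts. This stands as a possibility, so the result in steps 3 and 4 concerns the stated window and not every permitted date. But the clause sets no minimum and does not say whether it means earlier or later than the window.

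**Variability is acknowledged.** Section 10.3 expects it and Section 6.6 records it. The variation that 10.3 accepts is relative to the resection; it does not waive 6 months after the last intervention.

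**Arm-specific anchors are a coherent choice for an aesthetic outcome.** Three places agree on 3 to 8 months, and amending 10.3 would also remove the contradiction. That is fair as to the text. It would leave the two compared groups on different clocks, so the timing adjustment would then matter more.

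**The models are outlines.** The framework is longitudinal and W is open-ended. This stands: timing adjustment is unspecified.

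A reader might go further in three ways that the documents do not support:
- that 60% of Group B patients will be scored too early: the figure is a share of calendar width, and no visit distribution is given;
- that the primary contrast is biased, or biased toward one operation: no Q-score trajectory is given;
- that the plan rules out adjustment for time: it is silent.

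**Conclusion.** The contradiction is established from the text: a Group B visit that follows the schedule can break the rule in Section 10.3. When reconstruction is last, it affects the first 3 months of a 5-month window. It affects the whole window when adjuvant therapy ends more than 2 months after the last reconstructive procedure. The example of 9.2 to 11.5 and 12.0 to 14.3 months assumes that reconstruction is complete at mastectomy and that the Section 6.6 timings apply. How many patients follow that path is not given.

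The consequence is less certain than the contradiction. Late-score timing can differ between Groups A and B, and Models 1 and 2 do not say how it would be handled. Any bias in the contrast or the crossing point is of unknown size and direction and may be zero. The plan should be corrected, but the documents do not show that the primary result is compromised.

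**What to change.** 1. Reconcile Section 10.3 with Sections 6.5 and 8.0 and Appendices A and B, so that one stated anchor and one minimum for the final Breast-Q apply to both compared groups. Say which treatments count as an intervention for this purpose, consistently with the statement in Section 6.5 that Herceptin does not by itself shift study time points. If it did count and its one-year course began at or after surgery (an assumption), the minimum would be at least 12 + 6 = 18 months after surgery.
2. State whether the fallback clause permits earlier or later scores, and flag scores taken under it.
3. Confirm that the questionnaire date and treatment dates are captured on the existing Surgical Intervention, Oncology Course and Post-Operative Visit forms. Prespecify a sensitivity analysis of Models 1 and 2 that adjusts the late score for months since the last qualifying intervention.

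**Cost.** This is a short amendment with no new visit type or form. Some Group B questionnaires may come later, and some late enrolees may not reach the minimum before closure. Their number cannot be calculated, because the documents give no duration for staged reconstruction. From the end of recruitment to closure there are 58 − 41 = 17 months. A last enrolee operated on at enrolment whose final reconstruction falls more than 17 − 6 = 11 months after surgery would miss a 6-month minimum; an interval between enrolment and surgery shortens this. Adjusting for time also costs precision wherever group and timing remain correlated, which is a reason to align the timing and not rely on the model alone.

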10.4 Sample Size

Mammometrics will be converted to comparable data and then related to Q-Score as these are expected to be complex relationships.

We anticipate enrolling 83 subjects per study arm (166 total) with up to an additional 20 subjects undergoing mastectomy without reconstruction as a negative control for a total of 186 patients.

Initial plan is to use G*Power v 3.1, or a comparable statistical package. Based on an effect size $d=0.45$, Type I error $\alpha=0.05$, and power $(1-\beta) =0.8$, normal distribution, and 2-tails, we will require 83 subjects per arm (166 total). Assumptions: A difference in mean scores of 10 on a 100-point scale (Q-Score generated from Breast Q) was assumed to be significant. This is determined by assuming an SD of 20, with one-half of an SD being the threshold of discrimination for change in health-related quality of life.

Sample size calculations are based on 1) previously reported sample size calculations where data from the Breast Q for Breast Reconstruction was used with 2) the open-source statistical package G*Power 3.1.

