3.0 PATIENT SELECTION

3.1 Inclusion Criteria

- Patient must be scheduled to undergo breast conservation therapy (BCT), mastectomy or mastectomy with immediate reconstruction (defined as initiating the reconstructive process at time of mastectomy) for ductal carcinoma in situ (DCIS), lobular carcinoma in situ (LCIS), and early stage breast cancer (Clinical Stages IA-IIIB). Stage IIIB tumors are 2-5 cm with micrometastases 0.2 to 2.0 cm in lymph nodes; or 2-5 cm tumor with 1-3 positive axillary or internal mammary lymph nodes, or >5 cm with no lymph node involvement. Clinical staging, based on imaging and physical exam will be used for enrollment. Patients that are unexpectedly upstaged will be excluded at that time. For staging reference please see <http://www.cancer.gov/cancertopics/pdq/treatment/breast/patient/page2#keypoint13>.
- If multifocal/multicentric disease of the ipsilateral breast is encountered and patients are still deemed eligible for BCT or mastectomy per standard of care, then the tumor area will be calculated as the total volumes of the identified foci.
- Patient must be between 18-72 years old.
- Patient must be able to understand and willing to sign a written informed consent document.

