3.2 Exclusion Criteria

- Cognitive impairment
- History of radiation to the chest wall or breasts
- Patients unable to undergo MRI due to metallic implant or claustrophobia
- Patients that are pregnant since breast MRI is contraindicated
- History of previous breast surgery other than primary cosmetic augmentation or breast reduction
- Identification of a concurrent or synchronous contralateral cancer during the enrollment period
- Any patient that would not have been considered for BCT or reconstruction
- BCT patients planning to proceed with reconstruction during their study participation timeline.

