6.7 Criteria for Removal from Study

If the patient, at any time wishes to be removed from the study, they will be. This study does not propose any new interventions – it is an observational study of patients receiving normal, uninfluenced care for the treatment of breast cancer.

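### Section 10.4 enrols exactly the 83 per arm it requires, with no allowance for patients lost after enrolment, so 80% power at d = 0.45 is not assured for the evaluable sample

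*Combined protocol and SAP*

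**What the plan says.** Section 10.4 gives the planned enrolment: "We anticipate enrolling 83 subjects per study arm (166 total". Its next paragraph takes d = 0.45, two-sided alpha 0.05 and power 0.8 and concludes "we will require 83 subjects per arm (166 total". The further 20 patients who may be enrolled have mastectomy without reconstruction. They are a separate control group, not a reserve for the two compared arms. No section states an attrition rate, a non-evaluable fraction or a replacement rule.

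The protocol does provide for patients to leave after they are enrolled:

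- Section 3.1, where enrolment rests on clinical stage: "Patients that are unexpectedly upstaged will be excluded at that time".
- Section 3.2, among the exclusions: "Identification of a concurrent or synchronous contralateral cancer during the enrollment period".
- Section 6.7: "If the patient, at any time wishes to be removed from the study, they will be".

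Section 10.5 then plans a mixed model or GEE on Q-scores at baseline and two later times. Model 1 tests the group effect with control for the patient characteristics W.

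**The concern.** A sample-size calculation gives the number of patients needed in the analysis. Setting enrolment equal to that number assumes that nobody is lost. This protocol cannot assume that, because removal of upstaged patients is a written rule and withdrawal is always open.

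The late Breast-Q can also come long after surgery. On the longest intervals in section 6.6, radiotherapy after chemotherapy ends about 6 + 18 + 6 + 6 = 36 weeks after surgery. Section 6.5 then places the final BCT visit 6 to 18 months after radiation.

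At stake is how a null result is read. Readers would set it against 80% power at d = 0.45, a figure that the evaluable sample may not reach.

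**Working it through.** **Inputs.** From section 10.4: d = 0.45, two-sided alpha 0.05, target power 0.80, 83 per arm, a mean difference of 10 points and SD 20. Loss rates are assumed at 5% to 20%.

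**Reproducing 83.** For a two-sample comparison at d = 0.45:

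- The normal approximation gives 78 per arm and the exact t-test gives 79.
- A Wilcoxon-Mann-Whitney test with a normal parent distribution (n multiplied by 3/π = 0.955) gives exactly 83. That this test was used is an inference; section 10.4 names none.

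On the t-test the reserve is 83 − 79 = 4 per arm (4/83 = 4.8%). On the rank test there is none: power is 80.4% at 83 and 79.9% at 82.

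**Power after loss.** With n evaluable per arm, the noncentrality is δ = d√(n/2) on 2n − 2 degrees of freedom. Power is the probability that the noncentral t exceeds the two-sided 5% critical value in absolute size. At n = 83, δ = 0.45 × √41.5 = 2.90, the critical value is 1.975 and power is 82.2%. The detectable d is the value giving 80% power at that n; multiplied by 20 it is in Q-score points.

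| Evaluable per arm | Loss from 83 | Power, d = 0.45, t-test | Power, d = 0.45, rank test | Detectable d, t-test (points) | Power, d = 0.50, t-test |
|---|---|---|---|---|---|
| 83 | 0% | 82.2% | 80.4% | 0.44 (8.8) | 89.3% |
| 79 | 5% | 80.3% | 78.4% | 0.45 (9.0) | 87.8% |
| 75 | 10% | 78.2% | 76.3% | 0.46 (9.2) | 86.0% |
| 70 | 16% | 75.3% | 73.3% | 0.48 (9.5) | 83.6% |
| 66 | 20% | 72.8% | 70.8% | 0.49 (9.8) | 81.4% |

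The last column is there because 10 points at SD 20 is 10/20 = 0.50, not the 0.45 entered in the calculation. On the rank test, d = 0.50 with 66 per arm gives 79.5%.

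**Adjustment for W.** In a linear model, control for W multiplies the variance of the group effect by (1 − R² of Q on W)/(1 − R² of group on W). The effective n is therefore n(1 − R²group)/(1 − R²Q). The documents give neither R². With 75 per arm and d = 0.45:

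- R²group 0.2, R²Q 0.1: 75 × 0.8/0.9 = 66.7, power 0.73.
- R²group 0.2, R²Q 0.25: 75 × 0.8/0.75 = 80.0, power 0.81.
- R²group 0.1, R²Q 0.2: 75 × 0.9/0.8 = 84.4, power 0.83.

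The direction depends on the values assumed.

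**A dependency.** How many patients count as upstaged depends on the upper stage limit, which is IIIB in section 3.1 and IIB in section 10.3. The two must be reconciled before a loss rate can be estimated.

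**The case against.** The strongest reply is that loss may be small and is partly handled elsewhere:

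- Section 6.5 and the appendices accept the last available follow-up within the study period as the final visit, so a missed window does not by itself lose a patient.
- A post-operative Breast-Q is also taken at 1 to 10 weeks, and a mixed model or GEE can use patients who have only that score.
- Sections 6.1 and 6.3 describe the pre-operative Breast-Q as routine care.
- Section 10.2 keeps patients with complications.
- The contralateral-cancer exclusion is limited to the enrolment period.

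All of this stands, and it limits the loss. It does not clearly recover patients who are excluded for upstaging or who withdraw, and section 10.4 relies on none of it.

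A second reply is that, on the plan's own 10-point threshold, the t-test keeps about 81% power even at 20% loss. That also stands. The shortfall concerns the d = 0.45 to which the 80% is attached.

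Two stronger readings are tempting, and the documents support neither. A reader might infer that 80% power will definitely not be reached. With no loss rate given, and with 4 patients per arm in hand on a t-test, that cannot be shown. A reader might also infer that confounder adjustment costs further power. It may, if W predicts group strongly. But W, the baseline score and the repeated measures may explain enough outcome variance to raise power instead, as two of the three examples show.

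**Conclusion.** The point holds in a limited form. Enrolment equals the stated requirement, the protocol's own rules allow patients to leave after enrolment, and no allowance is made. The 80% power at d = 0.45 is therefore not assured for the patients who will be analysed.

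On an unadjusted t-test, a loss above about 5% takes power below 80%: to 78% at 10% loss and 73% at 20%. On the rank test that reproduces 83, any loss does so. The shortfall from 80% is thus about 2 to 7 percentage points on the t-test, or 4 to 9 on the rank test, for losses of 10% to 20%.

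These sizes rest on assumed loss rates and on an unadjusted comparison at a single time. The net effect of the adjusted longitudinal analysis on power cannot be fixed from the documents.

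**What to change.** Keep 83 enrolled per arm and restate section 10.4 for the expected evaluable number:

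1. Give the expected range of loss from exclusion, withdrawal and missing scores, with its basis. Over 5% to 20%, for example, 79 to 66 per arm remain. Unadjusted t-test power at d = 0.45 is then about 80% to 73%, and the difference detectable with 80% power is d of about 0.45 to 0.49 (9.0 to 9.8 points at SD 20).
2. Add that t-test power for the 10-point difference (d = 0.50) stays at about 81% or more across that range.
3. Name the test behind the 83.
4. State that the calculation is unadjusted, and that adjustment for W, the baseline score and the repeated measures may raise or lower power. Do not write in an expected variance inflation, since its direction is unknown.

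The cost is wording only: no extra patients and no change to the analysis. The one downside is that the stated power becomes slightly less favourable.
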